10.3.2 Cost-Effectiveness

The primary outcome for the cost-effectiveness analysis will be the incremental costeffective ratio (ICER) per disability-adjusted life-year (DALY) averted by 1HP versus 3HP. The incremental cost-effectiveness ratio is defined as (total cost 1HP – total cost 3HP) / (total DALYs averted 1HP – total DALYs averted 3HP). Similar ICER estimates will be calculated to compare incremental DALYs averted by 1HP and 3HP versus 6H and no treatment. Additionally, the cost per treatment completed and cost per adverse event averted will be calculated for 1HP and 3HP, alongside estimates of the ICER values for each of these secondary cost-effectiveness outcomes comparing all treatment strategies.

Cost-effectiveness will be estimated using a Markov model to simulate a population of individuals eligible for TPT under each treatment strategy. Cost and effectiveness parameters (e.g. treatment costs, adherence, treatment completion) for the model will be taken from empiric values observed at each health unit participating in the Curto study. One-way and multi-way sensitivity analysis will be used to evaluate cost-effectiveness on specific model parameters, including but not limited to: discount rate, currency conversion rate, cadre of staff providing services, price of rifapentine, 1HP and 3HP completion rates, and 1HP and 3HP efficacy. A probabilistic sensitivity analysis using Monte Carlo simulation will be used to simulate the Markov model across ranges of all input parameters and build estimates of uncertainty around each cost and cost-effectiveness outcome. For each iteration, the Monte Carlo simulation will sample with replacement from a beta distribution for all model parameters empirically observed across Curto health units, with the mode at the median value observed. Uncertainty will be presented as 95% uncertainty intervals, defined as the observed value at the 2.5th and 97.5th percentiles for each outcome across the Monte Carlo iterations.

Using the results of the Monte Carlo simulation, we will construct incremental costeffectiveness ratio planes and cost-effectiveness acceptability curves (CEACs) to demonstrate the probability of each strategy being cost-effective at different willingnessto-pay (WTP) thresholds. While we will consider a range of WTP thresholds in the primary analysis, we will use as our primary WTP threshold the most recent objective data on Brazil's country-specific WTP threshold. We will further report the probability of being cost-effective at WTP thresholds in \$500 increments (\$500, \$1000, etc). The ICER per DALY averted comparing 1HP to 3HP will be used for the primary ICER plane and CEAC.

Costs will be evaluated from the societal perspective, incorporating both costs to patients and to the healthcare system. Research costs will be excluded. Estimates of DALYs will be derived by combining literature values (TPT long-term effectiveness (Sterling, 2011), disability weights (Salomon, 2015)) with trial-based observations. We will use an analytic horizon of 5 years for tuberculosis events, with a lifetime horizon for TB-related sequelae, including death. The primary analysis will annuitize costs linearly using a 3% annual discount rate based on estimated life-years. In the analysis, costs will be presented in the latest year in which costs are measured during the trial, with costs collected in earlier years inflated using the World Bank's gross domestic product deflator for Brazil (https://data.worldbank.org/indicator/NY.GDP.DEFL.KD.ZG?locations=BR). All costs will then be converted to United States Dollars using the median World Bank conversion rate for that year (https://data.worldbank.org/indicator/PA.NUS.FCRF?locations=BR).

Time needed for care

As a part of economic data collection, time-and-motion (TAM) studies will be used to evaluate the time needed to provide comprehensive care for patients at each health unit. Sampling for TAM data collection will be stratified to ensure a broad coverage of visits by time of day, day of week, and time of year, plus inclusion of participants who require additional clinical evaluation (e.g., for side effects) so that the data represents a range of clinical operational conditions in our study setting. The TAM data will be analyzed and reported as median unit time with inter-quartile ranges (IQRs) per 1) discrete activity and 2) total health care staff person-time required (reported by types of personnel) for one patient throughout his/her LTBI care cascade (from initial diagnosis and clinical evaluations to treatment completion, inclusive of management of side effects). These time estimates will include both the direct (e.g. patient's face-to-face interaction with health care staff) and indirect (e.g. administrative efforts such as chart reviews and data reporting) efforts relevant for programmatic component of the patient event schedules of the Ultra Curto trial.

Time estimates will be presented separately for each health unit participating in the Ultra Curto trial. Differences in time requirements and cadre of staff completing activities across sites will be noted descriptively, but no formal statistical analysis will be performed to evaluate differences in time requirements across sites.

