7.2 Rationale

With support from the NIH and the CDC, we have pioneered the development of short-course, rifamycin-based TB preventive therapy (TPT) over the past 15 years. We have evaluated the efficacy of 3 months of weekly rifapentine and isoniazid (3HP) in people with and without HIV infection and showed that it is non-inferior to longer courses of INH, with better adherence and less toxicity. (Schechter 2006; Martinson 2011; Sterling 2011)

This regimen is now recommended as a first-line treatment for latent TB infection by the CDC and the World Health Organization, offering the potential of substantially increased uptake of TPT as part of the END TB Strategy. (WHO 2018)

More recently, supported by NIAID, we have shown that one month of daily rifapentine and isoniazid (1HP) is non-inferior to nine months of INH in people with HIV infection. (Swindells 2019) The availability of two innovative, new short-course TPT regimens offers a transformative opportunity to global TB control and achieving the End TB targets. However, a major question still requiring evidence is the safety of the 1HP regimen in people without HIV infection.

While the efficacy of 1HP can be assumed from its success in HIV-positive people, safety cannot. In the 1990s, several studies supported by NIAID and the CDC showed that a 2-month TBT regimen of rifampin and pyrazinamide (2RZ) was safe and efficacious in HIV-infected individuals.(Halsey 1998; Gordin 2000) However, subsequent research funded by NIAID, and experience in clinical practice, demonstrated that 2RZ was not safe in HIV-uninfected people, with high rates of hepatotoxicity and a number of deaths.(Schechter 2006; CDC 2001) No explanation for the difference in safety in HIV-infected and –uninfected people has ever been found, but this experience underscores the importance of demonstrating safety and tolerability in all target populations of new regimens for TBT.

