3.2 Primary Outcomes and Hypotheses

(1) Treatment success of TBT with \geq 90% adherence documented by self-report, pill count, and pharmacologic monitoring.

Hypothesis: Successful treatment with 1HP will be superior to 3HP, with 90% of individuals randomized to 1HP taking >90% of prescribed doses vs 80% of those on 3HP.

(2) Safety of treatment regimens, defined as occurrence of Grade 2 or higher targeted safety events and discontinuation of study medications because of side effects. Targeted safety events are hypersensitivity syndrome, rash, peripheral neuropathy, hepatotoxicity, nausea and vomiting, and drug-related fever.

Hypothesis: We hypothesize that the safety of 1HP will be superior to 3HP, with a rate of targeted adverse events or medication discontinuation of 6% vs. 13% for 3HP.

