3.3 Secondary Outcome and Hypothesis

(1) Incremental cost-effectiveness of 1HP and 3HP (compared to each other, 6H, and no treatment) using a societal perspective.

(2) Analyze, in each of the health units in the study, the time needed to provide comprehensive care to patients.

Hypothesis: We hypothesize that 1HP will be cost saving vs 3HP, vs modelled costs of 6H and vs no TPT.

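### SAP 10.3.2 sets the ICER's 95% uncertainty interval at simulation percentiles, which do not form an ordered interval if 1HP saves money as hypothesised

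*SAP*

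**What the plan says.** SAP 10.3.2 names the headline economic quantity: "The primary outcome for the cost-effectiveness analysis will be the incremental costeffective ratio (ICER) per disability-adjusted life-year (DALY) averted by 1HP versus 3HP". It is a ratio of two differences: "The incremental cost-effectiveness ratio is defined as (total cost 1HP – total cost 3HP) / (total DALYs averted 1HP – total DALYs averted 3HP", with the bracket closing there.

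The probabilistic analysis is to "build estimates of uncertainty around each cost and cost-effectiveness outcome", and the 95% uncertainty interval is "defined as the observed value at the 2.5th and 97.5th percentiles for each outcome across the Monte Carlo iterations". Read together, these sentences apply one percentile rule to costs and to ICERs alike. The same section plans further ICERs against 6H and no treatment, and ICERs per treatment completed and per adverse event averted.

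SAP 3.3 gives the expected direction of the numerator: "We hypothesize that 1HP will be cost saving vs 3HP". It expects savings against 6H and no treatment too.

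SAP 10.3.2 also plans ICER planes, acceptability curves, a Brazil-specific primary willingness-to-pay threshold, and probabilities of cost-effectiveness at $500 steps. It gives no rule for negative ICERs, for dominance, or for draws that fall in different quadrants. It plans no interval for net monetary benefit.

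**The concern.** A percentile interval means something only if moving along the scale means moving from worse to better, or the reverse. Incremental cost, incremental DALYs averted and net monetary benefit have that property. The ICER has it only while all draws lie in the dearer-and-better quadrant. The SAP expects them to lie elsewhere.

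Two things go wrong once the cost difference is negative. Draws with opposite meanings share the same value, and draws within the favourable quadrant are not ranked by merit. If the DALY difference can also pass through zero, the ratio becomes very large in both directions, and the interval can look uninformative when the conclusion is almost certain. The risk is that the main economic result is published with an interval that readers cannot interpret or will misread.

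**Working it through.** The documents give no ICER, cost difference, DALY difference or interval, so there is no plan figure to reproduce. The check has two parts: arithmetic on the definition, which needs no assumption about the trial, and a simulation to show size, which does.

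**1. The definition.** ICER = ΔC / ΔE, where ΔC is the cost difference and ΔE the difference in DALYs averted (1HP minus 3HP).

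- Opposite quadrants, negative sign. Cheaper and better: -20 / 0.01 = -$2,000. Dearer and worse: 20 / -0.01 = -$2,000.
- Opposite quadrants, positive sign. Dearer and better: 20 / 0.01 = +$2,000. Cheaper and worse: -20 / -0.01 = +$2,000.
- Inside cheaper-and-better, same $20 saving. ΔE = 0.01 gives -$2,000; ΔE = 0.001 gives -20 / 0.001 = -$20,000. The draw with one tenth of the health gain has the lower ICER.

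The last point applies even if every draw is cheaper and better.

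**2. Size, by simulation.**

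From the documents: success 90% for 1HP and 80% for 3HP (SAP 3.2) and 250 per arm (SAP 6), used for beta distributions of the success rates with household clustering ignored.

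Assumed, not in the documents: mean efficacy 0.80 with SD 0.04 to 0.08, 5-year TB risk 3%, 2 DALYs per case, ΔC normal with mean -$20 and SD $5, and willingness to pay λ = $1,000 per DALY.

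Formulas:

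- ΔE = (success₁ × efficacy₁ - success₃ × efficacy₃) × TB risk × DALYs per case
- Incremental net monetary benefit: INMB = λ × ΔE - ΔC

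At the means:

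- ΔE = (0.90 × 0.80 - 0.80 × 0.80) × 0.03 × 2 = 0.08 × 0.06 = 0.0048
- Ratio of means = -20 / 0.0048 ≈ -$4,167 per DALY
- INMB = 1,000 × 0.0048 + 20 = $24.8

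The SAP does not say whether efficacy is drawn once for both regimens or separately, so both are shown.

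| Efficacy draws | TB risk and DALYs per case | Draws with ΔE < 0 | ICER, 2.5th to 97.5th percentile |
|---|---|---|---|
| Shared, SD 0.04 to 0.08 | fixed | about 0.1% | about -$12,000 to -$1,800 |
| Separate, SD 0.04 | fixed | 7% | about -$37,000 to +$27,000 |
| Separate, SD 0.08 | fixed | 21% | about -$39,000 to +$36,000 |
| Shared, SD 0.08 | varied | 0.1% | -$14,406 to -$1,565 |
| Separate, SD 0.08 | varied | 21% | -$43,564 to +$39,573 |

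'Varied' means TB risk with SD 0.5 percentage points and DALYs per case from a gamma distribution with shape 16 and mean 2. The probability that INMB exceeds zero is above 0.99 in every row.

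In the last row the well-behaved quantities are: ΔC -$29.8 to -$10.2; ΔE -0.0072 to +0.0185; INMB $24.8 (9.3 to 41.3), with probability 0.998 of being positive. The same draws therefore give a near-certain conclusion and an ICER interval that runs from large negative to large positive values.

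**3. Other settings, with TB risk and DALYs varied and efficacy SD 0.08.**

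- If 3HP success were 87% and efficacy shared, 15% of draws would have ΔE < 0 and the percentiles would be -$159,018 to +$139,908.
- With a mean saving of only $5, 90% versus 80% success and separate efficacy, draws fall in all four quadrants: 67% cheaper and better, 17% cheaper and worse, 13% dearer and better, 3% dearer and worse.
- Across all scenarios run, the rank correlation between the ICER and DALYs gained among cheaper-and-better draws was +0.53 to +0.96. Larger health gains go with higher, apparently worse, ICERs.

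**The case against.** The strongest reply is that the plan already reports decision uncertainty in a valid way. The value of an acceptability curve at a threshold is the probability that net monetary benefit is positive there, and quadrant shares can be read off the plane. This stands. The fault lies in one stated interval and not in the whole uncertainty analysis, and the percentile rule is right for costs. But neither display changes the interval that the SAP attaches to its primary ICER.

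A reader might go further and infer that the DALY difference is near zero and will change sign between iterations. The documents do not say so. Planned success is "with 90% of individuals randomized to 1HP taking >90% of prescribed doses vs 80% of those on 3HP", which with equal efficacy implies a positive difference; the simulation then puts only about 0.1% of draws below zero. Crossing becomes common only with separate efficacy draws or closer success rates. Nor does Protocol 7.2 settle the matter. Its sentence "While the efficacy of 1HP can be assumed from its success in HIV-positive people, safety cannot" carries efficacy over from people with HIV, where the comparison was with nine months of isoniazid. It does not compare 1HP with 3HP. The ordering fault needs none of this: the cost-saving hypothesis is enough.

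Finally, Protocol 8.3, 15.2.2 and 15.8.4 place the economic work in a separate protocol or companion study that is not among the documents. It may contain rules for dominance. The SAP's rule is explicit all the same and should be right on its own terms.

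**Conclusion.** The point holds for the ICER interval. Under the SAP's hypothesis that 1HP is cost saving, the percentiles of the 1HP-versus-3HP ICER are not an ordered interval, because negative values mix opposite conclusions and misrank the favourable draws. This follows from the definition alone.

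The size is illustrative. It rests on assumed efficacy, TB risk, DALYs per case, costs and threshold, combined with the planned success rates. On those inputs the interval ranges from finite but misordered (about -$12,000 to -$1,800, shared efficacy) to spanning zero widely (about -$40,000 to between +$27,000 and +$36,000, separate efficacy, 7% to 21% of draws crossing). The probability of positive net benefit stays above 0.99 throughout.

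It would be too strong to say that the economic analysis cannot be interpreted, given the planned planes and curves. The matter concerns a secondary outcome; treatment success and safety are unaffected.

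**What to change.** Amend SAP 10.3.2 as follows:

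- Keep percentile intervals for costs. Report them also for incremental cost, incremental DALYs averted, and incremental net monetary benefit at the primary willingness-to-pay threshold.
- Report the share of draws in each quadrant of the plane.
- Give the ICER point estimate as the ratio of mean differences when the two means have the same sign. When both are negative, label it as the saving per DALY forgone: neither regimen dominates there, so it must not be reported as dominance.
- When the signs differ, state 'dominant' or 'dominated' in place of a negative ratio.
- Give no percentile interval for the ICER when draws are negative or span quadrants.

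The same wording should cover the other ICERs planned in that section. The cost is SAP text only. The simulation, its inputs and data collection do not change, and all the added quantities come from the same output.

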10.3.3 Tuberculosis

Incidence of active tuberculosis will be evaluated as an exploratory outcome. Incidence will be compared using Kaplan-Meier estimates at 24 weeks after enrolment and Greenwood's variance formula. This will be a sufficiently rare event that within-household correlation will be ignorable. Censoring will be at earliest of last study visit or death. As a sensitivity analysis, TB-free survival will also be analyzed.

REFERENCES

Kyung-Wook Jo 1, Ju Sang Kim 2, Hyouk-Soo Kwon 3, Yea Eun Park 1, Ja Young Kim 4, Min Jee Hong 4, Tae Sun Shim Adverse event and treatment completion rates of a 12-dose weekly isoniazid and rifapentine course for South Korean healthcare workers Respir Med 2019 Oct-Nov;158:42-48.

